15.2.1 All Adverse Events

The overall summary of AEs table will include the frequency (number and percentage) of participants with each of the following, tabulated by dose level and overall:

- TEAEs
- TEAEs with NCI-CTCAE Grade ≥ 3
- TEAEs with NCI-CTCAE Grade ≥ 4
- Related with M3258 TEAEs
- Related with M3258 TEAEs with NCI-CTCAE Grade ≥ 3
- Related with M3258 TEAEs with NCI-CTCAE Grade ≥ 4
- TEAEs leading to permanent discontinuation of M3258
- Related with M3258 TEAEs leading to permanent discontinuation of M3258
- Serious TEAEs
- Related with M3258 Serious TEAEs
- TEAEs leading to death (AEs with Grade 5 or outcome “fatal” if grade 5 not applicable)
- Related with M3258 TEAEs leading to death

Tables by SOC and PT will be tabulated by regimen, dose level and overall in a table displaying in separate columns and showing the incidence of TEAEs, by SOC and PT (both sorted alphabetically). This type of table by SOC and PT will be done for:

- All TEAEs
- related TEAEs
- Grade ≥ 3 TEAEs
- Related Grade ≥ 3 TEAEs
- TEAEs excluding SAEs (Clinical trial.gov and EudraCT -requirement)
- Also, TEAEs will be summarized by worst toxicity (according to NCI-CTCAE version 5.0) per participant, using preferred term as event category and primary system organ class (SOC). Analysis by worst toxicity will be provided by regimen, dose level and overall.

If an adverse event is reported for a given participant more than once during study intervention, the worst toxicity and the worst relationship to study intervention will be tabulated. In case a

participant had events with missing and non-missing grades, the maximum of the non-missing grades will be displayed.

A listing of all AEs will be provided. This listing will be sorted by study part, regimen, dose level and participant. This listing will additionally contain age, sex, type of myeloma, SOC, PT, grade, SAE (yes/no), DLT per investigator (yes/no), DLT per SMC, relatedness to M3258 (yes/no), start date (+treatment day), stop date (+treatment day), duration (in days), action taken with M3258, if treatment was stopped before start of AE: days since stop of treatment, and outcome.

Similarly, listing of all adverse events grade ≥ 3 (incl non TEAEs) and SAEs will be provided.

15.2.2 Adverse Events Leading to Study Intervention Discontinuation

A listing of TEAEs leading to treatment discontinuation, interruption, or dose reduction of each study drug will be provided. This listing, sorted by dose level and participant ID, will include: dose level, participant ID, age, sex, site of primary tumor, AE investigator term, SOC, PT, relationship to M3258 and dexamethasone (as applicable), seriousness, action taken with M3258 (displayed as: Disc/IR/DR), start date (+treatment day), stop date (+treatment day), duration (in days), if treatment was stopped before start of AE: days since stop of treatment, and outcome.

15.3 Deaths, Other Serious Adverse Events, and Other Significant Adverse Events

15.3.1 Deaths

A listing of Deaths will be provided, defined as any AE with Grade 5, or outcome "fatal" if grade 5 not applicable. This will be sorted by study part, regimen, dose level and participant. This listing will additionally contain age, sex, type of myeloma, SOC, PT, grade, SAE (yes/no), DLT per investigator (yes/no), relatedness to M3258 (yes/no), start date (+treatment day), stop date (+treatment day), duration (in days), action taken with M3258, if treatment was stopped before start of AE: days since stop of treatment, and outcome.

15.3.2 Serious Adverse Events

The listing of SAEs will also be provided with the relevant information with a flag for SAEs with onset outside of the on-treatment period.

15.3.3 Other Significant Adverse Events

A listing of AEs of special interest (AESI) will be provided. This will be sorted by dose level and participant. This listing will additionally contain age, sex, , SOC, PT, grade, SAE (yes/no), DLT

per investigator/SMC (yes/no), relatedness to M3258 (yes/no),, start date (+treatment day), stop date (+treatment day), duration (in days), action taken with M3258, if treatment was stopped before start of AE: days since stop of treatment, and outcome.

15.4 Clinical Laboratory Evaluation

Laboratory values (including corresponding normal ranges) from the local laboratories will be used B for summary statistics and shift tables.

Laboratory results will be classified according to the NCI-CTCAE criteria version 5.0. Some of the toxicity gradings are based on laboratory measurements in conjunction with clinical findings. Non-numerical qualifiers (with the exception of fasting flags) will not be taken into consideration in the derivation of CTCAE criteria (e.g., hypokalemia Grade 1 and Grade 2 are only distinguished by a non-numerical qualifier and therefore Grade 2 will not be derived).

Additional laboratory results that are not part of NCI-CTCAE will be presented according to the categories: below normal limit, within normal limits and above normal limit (according to the laboratory normal ranges).

Parameters with NCI-CTC grades available:

Hematology:

Hemoglobin (HB), Leukocytes (white blood cell decreased), Lymphocytes (lymphocyte count increased/decreased), Neutrophils / Absolute Neutrophils Count (ANC) (neutrophil count decreased), Platelet Count (PLT) (platelet count decreased).

Serum Chemistry:

Albumin (hypoalbuminemia), Alkaline Phosphatase (alkaline phosphatase increased), Alanine Aminotransferase (ALT) (ALT increased), Aspartate Aminotransferase (AST) (AST increased), Total Bilirubin (blood bilirubin increased, Cholesterol (cholesterol high), Creatinine (creatinine increased), Potassium (hypokalemia/ hyperkalemia), Sodium (hyponatremia/ hypernatremia), Magnesium (hypomagnesemia/hypermagnesemia), Calcium (hypocalcemia/ hypercalcemia), Glucose (hypoglycemia/hyperglycemia), Gamma Glutamyl Transferase (GGT) (GGT increased), Lipase (lipase increased), Phosphates (hypophosphatemia)

Parameters with NCI-CTC grades not available:

Hematology:

Hematocrit, Red Blood Cell (RBC), Reticulocytes, Mean Corpuscular Hemoglobin (MCH), Mean Corpuscular Volume (MCV), Mean Corpuscular Hemoglobin Concentration (MCHC).

Serum Chemistry:

C-Reactive Protein, Lactate Dehydrogenase (LDH), Total Protein, Total Urea, Uric Acid.

Coagulation: activated partial thromboplastin time (aPTT), Prothrombin time (PT) and prothrombin time (INR).

Urinalysis and microscopic urinalysis: all urinalysis parameters

Pregnancy test (not needed for end of dose escalation analysis)

The last measurement before study treatment (including unscheduled measurements) will serve as the baseline measurement.

Values below the detection limit will be imputed by half of the detection limit.

In case just a text value with an "> x" is reported it will be analyzed as +1 significant digit, e.g. "> 7.2 mmol" will be analyzed as 7.3.

For WBC differential counts (total neutrophil, lymphocyte, monocyte, eosinophil, and basophil counts), the absolute value will be used when reported. When only percentages are available (this is mainly important for neutrophils and lymphocytes, because the CTCAE grading is based on the absolute counts), the absolute value is derived as follows:

$$\text{Derived differential absolute count} = (\text{WBC count}) * (\text{Differential \%value} / 100)$$

If the range for the differential absolute count is not available (only range for value in % is available) then Grade 1 will be attributed to as follows:

- Lymphocyte count decreased:
 - derived absolute count does not meet Grade 2-4 criteria, and
 - % value < % LLN value, and
 - derived absolute count \geq 800/mm³
- Neutrophil count decreased
 - derived absolute count does not meet Grade 2-4 criteria, and
 - % value < % LLN value, and
 - derived absolute count \geq 1500/mm³

For calcium, CTCAE grading is based on Corrected Calcium and Ionized Calcium (CALCIO), if available. Corrected Calcium is calculated from Albumin and Calcium as follows

$$\text{Corrected calcium (mmol/L)} = \text{measured total Calcium (mmol/L)} + 0.02 (40 - \text{serum albumin [g/L]})$$

The time windows given in Table 4 will be applied to allocate measurements to treatment day. In case of multiple blood samples are collected in the same window, the value closest to the target day will be used for analysis. If there are two values with the same time before and after the target

day, the earlier value will be used for analysis. Windows only to be used for summary tables, not figures or listings

Table 4 Time windows for safety laboratory analysis

Treatment day	Window Definition
C1D1	No time window
C1D2	
C1D8	
C1D15	
C1D22	
C1D1	± 1 day
C1D8	
C1D15	
C1D22	
C3D1	
C3D15	
C4D1	
C5D1	± 3 days
C6D1	
CXD1 (after cycle 6)	± 7 days
End of Study Intervention (within 7 days after last intervention/intake)	± 3 days
Follow-up/Discontinuation (30 days after last dose)	± 7 days

Since the number of participants will decrease over time, time windows will not be applied for the complete treatment period (stopped after C6D1). For summaries by treatment day, the last available laboratory measurement will be presented in addition to the treatment day defined above.

Quantitative data will be summarized for actual values and absolute changes from baseline to each treatment day. The End of treatment visit will be summarized separately.

Qualitative data based on reference ranges will be described according to the categories (i.e. Low, Normal, and High). Abnormalities classified according to NCI-CTCAE toxicity grading version will be described using the worst on-treatment grade. For those parameters which are graded with two directions of toxicities such as potassium (hypokalemia/hyperkalemia), the toxicities will be summarized separately. Low direction toxicity (e.g., hypokalemia) grades at baseline and post baseline will be set to 0 when the variables are derived for summarizing high direction toxicity (e.g., hyperkalemia), and vice versa.

Parameters with NCI-CTC grades available:

The laboratory toxicities will be tabulated using descriptive statistics (number of participants and percentages) during the on-treatment period. The denominator to calculate percentages for each laboratory parameter is the number of participants evaluable for CTCAE grading (i.e. those participants for whom a Grade 0, 1, 2, 3 or 4 can be derived).

The summary of laboratory parameters by CTCAE grade table will include number and percentage of participants with Grade 1, 2, 3, 4, 3/4, and any grade (1 to 4), laboratory abnormalities during the on-treatment period.

The shift table will summarize baseline CTCAE grade versus the worst on-treatment CTCAE grade. The highest CTCAE grade during the on-treatment period is considered as the worst grade for the summary.

Parameters with NCI-CTC grades not available:

Hematology and chemistry evaluations which cannot be graded per CTCAE criteria will be summarized as frequency (number and row percentage) of participants with:

- shifts from baseline normal to at least one result above normal during on-treatment period
- shifts from baseline normal to at least one result below normal during on-treatment period

The coagulation parameters, urinalysis parameters, microscopic urinalysis parameters and pregnancy test will be listed in dedicated listings presenting all corresponding collected information on the eCRF.

The listings of laboratory results will be provided for all laboratory parameters. The listings will be sorted by parameters and assessment dates or visits for each participant. Laboratory values that are outside the normal range will also be flagged in the data listings, along with corresponding normal ranges and CTCAE grades..

The lab abnormalities \geq grade 3 will be also presented in a separate listing .

Line plots for Hematology

Graphical display (line plots) of neutrophils, platelets, lymphocytes and hemoglobin will be provided by actual time in days for all analyses. (with x-axis time, y-axis lab value), using different colors per regimen, dose level and different line types to identify participants

If available (and feasible due to potential differences between labs) reference lines for ULN and LLN should be added to the plots. Additionally treatment administration will be shown on the plot.

Hepatotoxicity assessment

A plot of peak ALT versus peak total bilirubin, both relative to the upper limit of normal (ULN) will be provided. This eDISH plot (evaluation of drug-induced serious hepatotoxicity) will have reference lines at $3 \times \text{ULN}$ for ALT and at $2 \times \text{ULN}$ for total bilirubin. Subjects outside the lower left box will be identified by subject-ID.

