- Hy's law: Evidence of hepatocellular toxicity without clear alternative reason to explain the observed liver-related laboratory abnormalities, such as increase in AST or ALT of ≥ 3 x

ULN elevation and elevation of serum total bilirubin $\geq 2 \times$ ULN, without initial findings of cholestasis (elevated serum ALP) or other apparent clinical causality (eg viral hepatitis A, B, C or co-medication)

- Any death not clearly due to the underlying disease or extraneous causes
- Any Grade ≥ 4 hematologic AE, and:
 - Grade ≥ 3 febrile neutropenia with ANC $<1000/\text{mm}^3$ and a single temperature of $>38.3^\circ\text{C}$ (101°F) or a sustained temperature of $\geq 38^\circ\text{C}$ (100.4°F) for more than 1 h
 - Grade ≥ 3 thrombocytopenia with medically concerning bleeding
 - Grade 4 thrombocytopenia lasting >7 days, or platelets $<10,000/\text{mm}^3$ at any time

Except:

- Isolated Grade 4 lymphopenia without clinical correlate
- Any Grade 4 neutropenia of < 7 days duration not associated with any clinical symptoms.

- Neuropathic Pain or Peripheral Sensory or Motor Neuropathy:
 - Any aggravation by 2 grades or any Grade ≥ 3 (severe symptoms: limiting self-care Activity of Daily Life [ADL]).
- Any TEAE the SMC deems clinically relevant, that impairs daily function or abnormality occurring in participants treated with M3258 -/+ combination with dexamethasone at any time in Cycle 1 and any toxicity at any time in Cycle 1
- A study intervention-related TEAE (observed in subsequent cycles) that in the opinion of the SMC is of potential clinical significance such that further dose escalation would expose participants to unacceptable risk.

Any DLT will be confirmed by the SMC.

Table 11 describes the recommended individual dose modifications related to M3258-related neuropathic pain or peripheral sensory or motor neuropathy when experienced by participants outside of DLT period. **Table 12** describes the individual dose modifications and temporary or permanent treatment discontinuations for M3258-related hematologic toxicities when experienced by participants outside of DLT period. **Table 13** describes the individual recommended temporary treatment discontinuations for M3258-related general toxicities when experienced by participants outside of DLT period.

Table 11 Recommended Dose Modification for New Onset or Worsening Neuropathic Pain and/or Peripheral Sensory or Motor Neuropathy (outside of DLT Period)

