Treatment cycles with M3258 -/+ combination with dexamethasone will be repeated every 21 or 28 days; hence, for a cycle of treatment to begin, the participant's blood ANC must be \geq 1,000 mm³ and the platelet count must be \geq 75,000 mm³. Additionally, all other toxicities considered to be related to study intervention must have resolved to \leq Grade 1 or to the participant's Baseline value.

If the participant fails to meet the above-cited criteria for treatment, re-initiation of the next cycle of treatment should be delayed for one week. At the end of which, the participant should be re-evaluated to determine whether the criteria for re-treatment have been met. If a delay in the initiation of the next cycle of more than two weeks is required because of incomplete recovery from toxicity, then this event should be considered a DLT. If toxicity does not resolve by two weeks, then the participant should be discontinued from the study. This decision will be made in the context of emerging clinical data and in consultation with Sponsor Medical Responsible. If, in the opinion of the Investigator and the Sponsor Medical Responsible, it is in the participant's best interest to continue the treatment with M3258 -/+ combination with dexamethasone, the study intervention will only be resumed after recovery from toxicity to \leq Grade 1 or Baseline values. Additionally, the dose of study intervention should be reduced by at least 1 dose levels. If the DLT recurs upon resuming study intervention at a lower dose, the study intervention should immediately be discontinued. For the first study cohort, no dose reduction will be allowed.

7

Discontinuation of Study Intervention and Participant Discontinuation/Withdrawal

7.1

Discontinuation of Study Intervention

Stopping Rules for Individual Participants:

The Investigator must consider discontinuation of study intervention for abnormal liver function when a participant meets one of the conditions outlined in Section 6.6 or if the Investigator believes that it is in best interest of the participant.

All events of ALT \geq 3 \times ULN and bilirubin \geq 2 \times ULN ($> 35\%$ direct bilirubin) or ALT $>$ 3 \times ULN and international normalized ratio (INR) $>$ 1.5, if INR measured, may indicate potential severe liver injury (possible Hy's Law) and must be reported as an AE and SAE.

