Appendix 6 Liver Safety: Suggested Actions and Follow-Up Assessments

If a study participant is noted to have ALT or AST elevated $> 3 \times$ ULN (new or worsening of preexisting), the abnormality should be recorded as an AE, regardless if clinical symptoms are present or not. If a study participant is noted to have ALT or AST > 3 times ULN and total bilirubin > 2 ULN for which an alternative etiology has not been identified, the event should be reported as a SAE. The Investigator must contact the Sponsor Medical Responsible for discussion.

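### The one display that combines liver tests plots ALT against bilirubin, so participants who meet a protocol liver rule through AST or INR are labelled but not placed in the Hy's law quadrant or identified as meeting the rule (minor)

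*SAP*

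**What the plan says.** Under the hepatotoxicity heading of SAP 15.4 there is a single figure: "A plot of peak ALT versus peak total bilirubin, both relative to the upper limit of normal (ULN) will be provided". Its reference lines are at 3 × ULN for ALT and 2 × ULN for total bilirubin, and "Subjects outside the lower left box will be identified by subject-ID". Section 15.5 of the SMC analysis plan specifies the same figure.

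The protocol states liver criteria in three places:

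- Section 6.6 (DLT) describes abnormalities "such as increase in AST or ALT of" at least 3 × ULN, with total bilirubin at least 2 × ULN and without initial cholestasis or another apparent cause.
- Section 7.1 covers ALT at least 3 × ULN with bilirubin at least 2 × ULN (more than 35% direct), or ALT above 3 × ULN with INR above 1.5 where INR was measured. It says that these events "may indicate potential severe liver injury (possible Hy's Law) and must be reported as an AE and SAE".
- Appendix 6 makes an SAE of "ALT or AST > 3 times ULN and total bilirubin > 2 ULN" where no alternative etiology has been identified.

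Elsewhere in SAP 15.4, AST is CTCAE-graded and so enters the grade summary and shift table. Coagulation results, including INR, are listed, and so are all other laboratory parameters.

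**The concern.** A plot of this kind is read by quadrant: the upper right is where one looks for potential Hy's law cases. If the protocol's rule can be met through a test that is on neither axis, the quadrant and the rule no longer match. A reader of the report who counts the upper-right points gets the number with high ALT and high bilirubin, which need not be the number who meet the protocol's own laboratory limits.

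No other planned output makes that count. The AST tables take one parameter at a time, INR is not joined to ALT, and the DLT and SAE listings show events that someone has already recognised and recorded. What is at stake is a laboratory-based cross-check on that recognition, for a harm that the protocol treats as dose-limiting or serious.

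**Working it through.** No sample size or error rate is involved. The check sets each rule against the axes of the plot and then classifies illustrative participants.

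**Rules side by side**

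| Source | Enzyme | Partner test | Other conditions |
|---|---|---|---|
| Protocol 6.6 (DLT) | AST or ALT ≥ 3 × ULN | bilirubin ≥ 2 × ULN | no cholestasis, no other cause |
| Protocol 7.1 (SAE), first limb | ALT ≥ 3 × ULN | bilirubin ≥ 2 × ULN | > 35% direct bilirubin |
| Protocol 7.1 (SAE), second limb | ALT > 3 × ULN | INR > 1.5 | if INR measured |
| Appendix 6 (SAE) | ALT or AST > 3 × ULN | bilirubin > 2 × ULN | no alternative etiology |
| SAP plot | ALT, line at 3 × ULN | bilirubin, line at 2 × ULN | none |

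The rules differ in the enzymes named, in ≥ against >, and in the direct-bilirubin and INR conditions. The INR limb is in Section 7.1 alone, and Section 7.1 does not name AST.

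**Illustrative participants.** The values are assumptions, in multiples of ULN except INR. ALT is taken as the horizontal axis. Only the enzyme, bilirubin and INR limits are applied; the other conditions are taken as met.

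| Case | ALT | AST | Bilirubin | INR | 6.6 | 7.1 | App. 6 | Quadrant | Labelled |
|---|---|---|---|---|---|---|---|---|---|
| A | 4 | 2 | 2.5 | 1.0 | yes | yes | yes | upper right | yes |
| B | 2 | 4 | 2.5 | 1.0 | yes | no | yes | upper left | yes |
| C | 4 | 2 | 1.2 | 1.8 | no | yes | no | lower right | yes |
| D | 2 | 4 | 1.2 | 1.8 | no | no | no | lower left | no |

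B meets the DLT and Appendix 6 limits through AST but is plotted as bilirubin only. C meets Section 7.1 through INR but is plotted as ALT only. Both are labelled, because the AST route needs bilirubin at or above its line and the INR route needs ALT above its line. The unlabelled case, D, meets no rule. Values exactly on a line are the one ambiguity: the SAP does not say to which box they belong.

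**Does the label identify the case?** Inclusion criterion 6 accepts bilirubin below 3 × ULN in documented Gilbert's syndrome. Such a participant at 2.5 × ULN with normal AST and ALT lies in the same quadrant as B and carries the same kind of label. The criterion also allows baseline ALT up to 3.0 × ULN, so a small rise moves a participant into C's quadrant. The plot cannot separate these from participants who meet a rule.

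**What the SMC had.** Section 15.5 of its plan limits laboratory outputs to patient profiles, this plot and line plots of four hematology parameters. The plot was therefore its only cross-participant liver display. AST and INR could be read in the individual profiles, which include biochemistry and coagulation (Section 15.2).

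**The case against.** The strongest reply is that no participant is lost. A reader might infer that someone who qualifies through AST or INR is shown as not being a case. The documents do not support that, since everyone outside the lower left box is identified by subject ID and the cases above all lie outside it.

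A reader might also infer that this plot is all the hepatotoxicity analysis there is. It is not. AST has grade and shift tables, all laboratory values are listed with out-of-range flags, and abnormalities of grade 3 or higher have their own listing. Appendix 6 requires AST or ALT above 3 × ULN to be recorded as an AE, and the combined events in Section 7.1 and Appendix 6 are reportable as SAEs.

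Nor can one infer that DLTs are undercounted. The investigator or sponsor assesses them, the SMC confirms them and SAP 15.1 tabulates them by those judgements, so the Bayesian model input does not depend on the plot. The laboratory limits alone do not make a DLT in any case, because Section 6.6 also requires that cholestasis and other causes be absent.

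All of this stands, and it makes the point minor. What it does not supply is any output that applies a combined liver rule to the laboratory data. The SAP does this for ECG: Section 15.6 counts and flags participants by compound criteria such as low heart rate together with a set decrease from baseline.

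**Conclusion.** The point holds as a minor mismatch between a display and the rules it should reflect. One of three biochemical routes reaches the Hy's law quadrant; the other two are labelled but neither placed there nor identified as meeting a rule. Primary DLT results are unaffected, and a careful reader can recover every case from the listings. The documents give no rate for AST-only or INR-only cases, so no percentage can be attached. The trial is small and descriptive, and SAP Section 7 reports that it stopped before Part A reached its primary objective, so such cases may be few or absent. The conclusion assumes that the plot is read by its quadrants, as its reference lines invite.

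Separately, Protocol 6.6, Protocol 7.1 and Appendix 6 do not agree with one another and must be reconciled by the sponsor. This review does not say which is right.

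**What to change.** In SAP 15.4, and in Section 15.5 of the SMC plan if it is used again, plot the peak of the higher of ALT/ULN and AST/ULN against peak total bilirubin/ULN. Keep the same reference lines and use a symbol to show whether ALT or AST drives the point. State to which box a value on a line belongs.

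Add a short listing, with counts, of participants who meet each protocol liver criterion as written in Section 6.6, Section 7.1 and Appendix 6. Keep the criteria in separate columns, and show baseline AST, ALT, bilirubin and ALP so that Gilbert's syndrome and raised baselines are visible. Separate columns avoid choosing between the passages before they are reconciled.

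The cost is one changed figure and one added listing. AST, ALT, ALP, total and indirect bilirubin and INR are all in the Appendix 7 panels, and direct bilirubin follows as total minus indirect. The drawback is that AST is less liver-specific, so a few non-hepatic rises may appear in the upper right quadrant; the symbol lets a reader discount them.
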